5.3 Exclusion criteria

Patients eligible for this study must not meet **any** of the following criteria:

1. Creatinine clearance below the contraindication limit in the locally approved prescribing information.
2. Serum creatinine level > 1.5 x ULN (upper limit of normal)
3. AST (SGOT) /ALT (SGPT) > 5 x ULN, unless LIC confirmed as >10 mg Fe/dw within 6 months prior to screening visit.
4. Significant proteinuria as indicated by a urinary protein/creatinine ratio > 0.5 mg/mg in a non-first void urine sample.
5. Patients with significant impaired gastrointestinal (GI) function or GI disease that may significantly alter the absorption of oral deferasirox (e.g. ulcerative diseases, uncontrolled nausea, vomiting, diarrhea, malabsorption syndrome, or small bowel resection).
6. Clinical or laboratory evidence of active Hepatitis B or Hepatitis C (HBsAg in the absence of HBsAb OR HCV Ab positive with HCV RNA positive).

7. Patients with psychiatric or addictive disorders which prevent them from giving their informed consent or undergoing any of the treatment options or patients unwilling or unable to comply with the protocol.
8. Patients with a known history of HIV seropositivity (Elisa or Western blot).
9. History of malignancy of any organ system, treated or untreated, within the past 5 years whether or not there is evidence of local recurrence or metastases, with the exception of localized basal cell carcinoma of the skin.
10. Patients participating in another clinical trial or receiving an investigational drug. Patients who have recently completed treatment with an investigational product must have ceased this treatment for at least five times the half-life of the investigational product.
11. History of hypersensitivity to any of the study drug or excipients.
12. Significant medical condition interfering with the ability to partake in this study (e.g. systemic uncontrolled hypertension, unstable cardiac disease not controlled by standard medical therapy, systemic disease (cardiovascular, renal, hepatic, etc.).
13. Women of child-bearing potential, defined as all women physiologically capable of becoming pregnant, **unless** they are using effective methods of contraception during dosing of study treatment. Effective contraception methods include:

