10.1 Analysis sets

The following analysis sets will be used in this trial.

Enrolled Set

The Enrolled Set comprises of all patients enrolled in this study.

Full Analysis Set

The Full Analysis Set (FAS) comprises all patients to whom study treatment has been assigned and who received at least one dose of each study treatment (DT and FCT). Patients will be analyzed according to the treatment they have been assigned to.

Safety set

The Safety Set includes all patients who received at least one dose of either study treatment (DT or FCT), and at least one safety assessment on or after Day 1.

Patients will be analyzed according to the study treatment received, where treatment received is defined as the assigned treatment if the patient took at least one dose of that treatment or the first treatment received if the assigned treatment was never received.

Per-Protocol set

The Per-Protocol Set (PPS) consists of a subset of the patients in the FAS who are compliant with requirements of the CSP (clinical study protocol) without any major protocol deviation.

The major protocol deviations that will lead to exclusion of patients from the PPS will be detailed in the SAP.

Pharmacokinetic analysis set

Not applicable

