## 2.2 Analysis sets

The following analysis sets will be used in this study.

**Enrolled Set:** The Enrolled Set comprises all patients enrolled in this study. Patients who discontinued from the study due to ineligibility immediately after Visit 2 are not considered as enrolled.

**Full Analysis Set (FAS):** The Full Analysis Set comprises all patients to whom study treatment has been assigned and who received at least one dose of each study treatment (DT and FCT). Patients will be analyzed according to the treatment they have been assigned to.

**Safety Set (SAF):** The Safety Set includes all patients who received at least one dose of either study treatment (DT or FCT), and at least one safety assessment on or after Day 1.

Patients will be analyzed according to the study treatment received, where treatment received is defined as the assigned treatment if the patient took at least one dose of that treatment or the first treatment received if the assigned treatment was never received.

**Per-Protocol Set (PPS):** The Per-Protocol Set consists of a subset of the patients in FAS who are compliant with requirements of the clinical study protocol (CSP) without any major protocol deviation.

Any major protocol deviation will lead to exclusion of patients from PPS. The list of PDs is defined in [Section 5.5](#).

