## 2.8 Safety analyses

For all safety analyses, the Safety Set (SAF) will be used. All listings and summaries will be presented by treatment group (wherever applicable) and by TDT and NTDT. In addition, all key safety summaries will be reported separately for all age groups (defined earlier in [Section 2.2.1](#)). The safety analysis will also be presented separately for core and extension phases of the study.

The overall observation period will be divided into three mutually exclusive segments:

1. Pre-treatment period: from day of patient's informed consent to the day before first dose of study medication.
2. On-treatment period: from day of first dose of study medication to 30 days after last dose of study medication.
3. Post-treatment period: starting at day 30+1 after last dose of study medication.

All serious adverse events (SAEs), non-serious adverse events (AEs) and adverse events of special interest (AESI) which are specific gastrointestinal events during the on-treatment period will be summarized.

All data, regardless of observation period, will be listed. Safety assessments starting during the pre-treatment or post-treatment period will be flagged in the listings. Safety assessments starting prior to study day 1 will appear with negative study day in the listings.

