An overall summary of type of AEs (e.g. serious, leading to study drug discontinuation, requiring dose adjustment and/or interruption) will be presented by treatment (overall and severe). This summary as well as the incidence of AEs (overall and severe), regardless of study drug relationship, will additionally be provided separately for pediatric and adult patients. AEs will be summarized by presenting the number and percentage of patients having at least one AE, and having at least one AE by system organ class and/or preferred term, severity, and relation to study drug by treatment. A patient with multiple occurrences of an AE will be counted only once in the AE category.

All AEs, deaths and SAEs (including those from the pre and post-treatment periods) will be summarized and listed and those collected during the pre-treatment and post-treatment period will be flagged. Severity of AEs will be assessed as mild, moderate, or severe.

Separate summaries will be provided for deaths, SAEs, other significant AEs leading to discontinuation, and AEs leading to dose adjustment (including study treatment discontinuation).

A graphical display of relative frequencies within system organ classes and risks difference = risk in FCT-risk in DT (because if in DT, patient count for some SOC becomes 0, then relative risk will be undefined), as appropriate, may be presented by forest plot.

The following formula will be used:

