| E06a                | Hepatitis B or Hepatitis C tests were not performed at visit 1.  | INCLUDE IN EVERYTHING        | 0                    |
| E07                 | Clinical or laboratory evidence of active Hepatitis B or C at visit 1.   | EXCLUDED FROM PPS            | 4                    |
| E08                 | Known history of HIV seropositivity (Elisa or Western blot).   | EXCLUDED FROM PPS            | 4                    |
| E9                  | History of malignancy of any organ system, treated or untreated, within the past 5 years (protocol section 5.3)  | EXCLUDED FROM PPS            | 4                    |
| E10                 | Patients participating in another clinical trial or receiving an investigational drug.   | EXCLUDE FROM FAS             | 1                    |
| E11                 | History of hypersensitivity to any of the study drugs or their excipients  | EXCLUDED FROM PPS            | 4                    |
| E12                 | Significant medical condition interfering with the ability to take part in this study  | EXCLUDE FROM PPS             | 4                    |
| E13                 | Female of child bearing potential unwilling to use contraception as requested by the protocol  | INCLUDE IN EVERYTHING        | 0                    |
| E14                 | Female not meeting post-menopausal criteria stated in the protocol and not using the contraception methods requested in the protocol   | INCLUDE IN EVERYTHING        | 0                    |
| E15                 | Female of child bearing potential with a positive serum pregnancy in the screening visit however subject is enrolled into the study  | EXCLUDE FROM PPS             | 4                    |
| E16                 | Sexually active males not using condom during intercourse while taking drug and for 28 days after stopping study medication  | INCLUDE IN EVERYTHING        | 0                    |
| E17                 | Patients with psychiatric or addictive disorders preventing from giving informed consent or undergoing any of the treatment options or unable or unwilling to comply with the protocol | EXCLUDE FROM FAS AND SAF     | 3                    |

| Deviation ID | Description of Deviation   | Exclusion in Analyses | Severity code |
|---------------------|---|------------------------------|----------------------|

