**Table 3 Population code text**

| Population Code | Population code text                 |
|-----------------|--------------------------------------|
| 0               | INCLUDE IN EVERYTHING                |
| 1               | EXCLUDE FROM FULL ANALYSIS SET (FAS) |
| 2               | EXCLUDE FROM SAFETY SET (SAF)        |
| 3               | EXCLUDE FROM FAS AND SAF             |
| 4               | EXCLUDE FROM PER-PROTOCOL SET (PPS)  |
| 6               | EXCLUDE FROM SAF AND PPS             |

Unless otherwise stated, summary tables, figures and listings will be on all subjects included in the analysis set under consideration.

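### SAP deviation code E17 can remove dosed, validly consented patients from the Safety Set, contradicting its definition in SAP 2.2 and protocol 10.1

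*SAP*

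**What the plan says.** Protocol 10.1 and SAP 2.2 define the Safety Set in the same terms. The SAP states that "The Safety Set includes all patients who received at least one dose of either study treatment (DT or FCT"; the rest of the sentence adds one safety assessment on or after Day 1. Neither document attaches a deviation-based exclusion to this set. Deviations are tied to the Per-Protocol Set: protocol 10.1 says "The major protocol deviations that will lead to exclusion of patients from the PPS will be detailed in the SAP", and SAP 2.2 likewise sends major deviations to the PPS and points to SAP 5.5 for the list.

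SAP 5.5 goes further. Table 1, row E17, starts from a mental-health or addiction problem, which it describes as "preventing from giving informed consent or undergoing any of the treatment options or unable or unwilling to comply with the protocol"; the action assigned is "EXCLUDE FROM FAS AND SAF", code 3. Table 2 drops codes 2, 3 and 6 from the Safety Set and codes 1 and 3 from the FAS.

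SAP 2.8 then states: "For all safety analyses, the Safety Set (SAF) will be used". The note under Table 3 adds: "Unless otherwise stated, summary tables, figures and listings will be on all subjects included in the analysis set under consideration". SAP 4 records no change to the protocol-specified analyses.

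**The concern.** A deviation code has an effect on the Safety Set only if the patient was dosed, because an undosed patient is outside the set already. For a dosed patient coded E17 with at least one safety assessment, SAP 2.2 says in and SAP 5.5 says out. A programmer working from Tables 1 and 2 would take the patient out.

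E17 is also broader than a consent failure. Protocol exclusion criterion 7, which it restates, lists psychiatric or addictive disorders and then, as a separate limb, "or patients unwilling or unable to comply with the protocol". Inability or unwillingness to comply does not invalidate consent. Unlike E01, E02, E04, E05 and E07, the E17 row is not tied to screening or Visit 1, so nothing in it prevents the judgement from being made after dosing and after an adverse event.

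Overall safety of FCT compared with DT is a secondary objective. At stake is whether its tables cover all treated patients, as both documents say they should.

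**Working it through.** No figure in the plan depends on this rule, so the check is of the exclusion chain.

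**Step 1: follow the codes.** E17 is code 3 (Table 1). Code 3 is in the Safety Set exclusion list {2, 3, 6} and the FAS exclusion list {1, 3} (Table 2). E17 therefore removes the patient from both. It also removes the patient from the PPS, which is defined as a subset of the FAS.

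**Step 2: find every row that reaches the Safety Set.** No row of Table 1 uses code 2 or code 6, so only code 3 matters. Four rows carry it:

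| Row | Subject of the row | Dosed with valid consent? |
|---|---|---|
| D02 | No study treatment received | No: undosed by definition |
| I01a | Consent form not obtained from subject | No: consent absent |
| I01b | Consent form not obtained from parent or representative | No: consent absent |
| E17 | Disorder, or unable or unwilling to comply | Possible |

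**Step 3: compare other entry violations.** Raised creatinine (E02), impaired GI function (E05), active hepatitis (E07), hypersensitivity history (E11), significant medical condition (E12) and positive screening pregnancy test (E15) are all code 4, PPS only. Concurrent trial participation (E10) is code 1, FAS only. Patients with any of these stay in the Safety Set.

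**Step 4: check for overlap.** Protocol 7.1.3.1 makes unwillingness to comply, including with study treatment, a reason for withdrawal. A patient who meets it and is not discontinued falls under D04, code 4. The E17 wording could describe the same patient at code 3. The SAP gives no order of precedence.

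**Step 5: trace the outputs.** Exposure (SAP 2.4.1) and all safety analyses (SAP 2.8) use the Safety Set, so their summaries lose the patient. Listings are less clear. SAP 2.8 says all data will be listed regardless of observation period, and SAP 2.8.1 says: "All AEs, deaths and SAEs (including those from the pre and post-treatment periods) will be summarized and listed". The restriction under Table 3 yields where something else is stated. Either text could be taken to govern.

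**Step 6: illustrate the size.** These counts are assumed: 145 dosed (the planned enrolment), 10 with an SAE, and k patients coded E17 and removed.

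| k | All k had an SAE: (10 − k)/(145 − k) | None had an SAE: 10/(145 − k) |
|---|---|---|
| 0 | 10/145 = 6.90% | 10/145 = 6.90% |
| 1 | 9/144 = 6.25% | 10/144 = 6.94% |
| 3 | 7/142 = 4.93% | 10/142 = 7.04% |
| 5 | 5/140 = 3.57% | 10/140 = 7.14% |

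The reported rate can move either way. It falls only if the removed patients had events more often than the rest.

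**The case against.** **E17 is an entry criterion.** Eligibility is checked before drug is provided (protocol 7.1.1.1) and again on Day 1 before dosing (7.1.1.3), and on-treatment unwillingness has its own withdrawal criterion and deviation code. The natural E17 case is thus a patient ineligible at entry who was dosed in error. This stands. A reader might infer that patients who stop because of intolerance will be coded E17, so that safety is made to look better. The documents do not say so; the missing time limit only leaves it possible.

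**The patient does not vanish from all reporting.** A reader might infer that E17 patients' events drop out of every safety output. The documents do not support that: the listing statements in SAP 2.8 and 2.8.1 can be read as keeping them. SAE reporting to the sponsor (protocol 8.2.2) is unaffected, significant deviations go into the CSR (protocol 12), and disposition uses the Enrolled Set. That last backstop is partial, because SAP 2.2 does not count as enrolled a patient who discontinues for ineligibility immediately after Visit 2, the Day 1 visit. None of these replaces the Safety Set summaries.

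**One limb concerns consent.** Where a disorder prevented valid consent, code 3 matches I01a and I01b. This stands, and it means that recoding the whole row would go too far.

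**The expected effect is small.** Two eligibility checks must fail before the rule acts, and SAP 2.7.2 plans no formal testing of secondary endpoints. That limits the likely size but does not resolve the contradiction.

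**Conclusion.** The contradiction is real and can be read directly from the text: the appendix removes patients whom the Safety Set definition includes, through a single row that is out of line with comparable entry violations. A dosed, validly consented patient coded E17 would be lost from the Safety Set summaries, with listings ambiguous.

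The size is unknown. The documents give no E17 count, and if there are none the rule changes nothing. The percentages above rest on assumed counts and show scale only. Bias in favour of study treatment is not established. Nor is any change to the primary result, although code 3 also removes E17 patients from the FAS on which the preference analysis is based.

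**What to change.** 1. Split E17 in SAP 5.5 Table 1. Route cases without valid consent to I01a/I01b, code 3, with wording that covers a form signed without capacity. Give the remaining limbs (unable to undergo treatment; unable or unwilling to comply) code 4, PPS only. They then agree with D04, so precedence no longer matters for the analysis sets.
2. Add to SAP 2.2 that no dosed patient with valid consent who meets the Safety Set definition is removed from it because of a protocol deviation.
3. State in SAP 2.8 that adverse event, SAE and death listings cover all dosed patients with valid consent.
4. Record the consequence for the primary analysis: under code 4 these patients return to the FAS if they received both DT and FCT, in line with the FAS definition.

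The cost is one row divided in two and a few sentences, with no new data. The SAP history shows that the interim lock preceded the current version. If any patient had been coded E17 by then, the affected core-phase outputs would need rerunning.

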## 2 Statistical methods

### 2.1 Data analysis general information

All analysis will be performed by NBS CONEXTS, Novartis.

It is planned that the data from all centers that participate in this study will be used for analysis. Analysis datasets and statistical outputs will be produced using the most recent SAS® Version 9.4 (SAS Institute Inc., Cary, NC, USA), and stored in Novartis global programming & statistical environment (GPS).

As the primary endpoint analysis will be performed at Week 48, there will be a database lock after all patients have completed Week 48 assessments. The proposed statistical analysis for interim analysis is described in [Section 2.14](#). A final database lock will occur when all patients have completed the study.

All summary statistics for continuous variables will include n (number), mean, standard deviation (SD), median, lower and upper quartiles (Q1, Q3), minimum, maximum, and, where applicable, the estimate and the 95% confidence intervals (CI) of mean. For categorical variables, descriptive statistics will include the number (frequencies) and percentage of patients in each category. Summary statistics will also be presented graphically wherever applicable.

If not otherwise specified, p-values and CI will be presented as two-sided. Unless otherwise stated, the default level of significance will be set to 5% (two-sided, family-wise type-I-error).

All data analysis will be presented by treatment group, i.e. DFX DT and DFX FCT, iron chelation status (naïve or pre-treated) and by thalassemia transfusion status (TDT or NTDT), wherever applicable. Efficacy and safety data for the core and extension phases will also be presented by the above groups. Since this study also includes pediatric patients, all key safety and efficacy endpoints will also be summarized by the age groups as defined in the protocol and [Section 2.2.1](#).

The analysis will be conducted on all patients' data at the specific time-points (Week 4, 24, 28, and 48), wherever applicable and at the time the study (both core and extension phases) ends.

Unless otherwise specified, if there are additional data available for any assessment (for example data on unscheduled visit) then the average of the available values will be presented under the dedicated visit.

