
Visit 20 Date of visit should be 476 days from Visit 2 also consider buffer +/-7 days (e.g. Timeframe to do the visit is 469 days to 483 days)

Visit 21 Date of visit should be 504 days from Visit 2 also consider buffer +/-7 days (e.g. Timeframe to do the visit is 497 days to 511 days)

Visit 22 Date of visit should be 532 days from Visit 2 also consider buffer +/-7 days (e.g. Timeframe to do the visit is 525 days to 539 days)

Visit 23 Date of visit should be 560 days from Visit 2 also consider buffer +/-7 days (e.g. Timeframe to do the visit is 553 days to 567 days)

Visit 24 Date of visit should be 588 days from Visit 2 also consider buffer +/-7 days (e.g. Timeframe to do the visit is 581 days to 595 days)

Visit 25 Date of visit should be 616 days from Visit 2 also consider buffer +/-7 days (e.g. Timeframe to do the visit is 609 days to 623 days)

Visit 26 Date of visit should be 644 days from Visit 2 also consider buffer +/-7 days (e.g. Timeframe to do the visit is 637 days to 651 days)

Visit 777 Date of visit should be 672 days from Visit 2 also consider buffer +/-7 days (e.g. Timeframe to do the visit is 665 days to 679 days)

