### **2.5.1 Primary endpoint**

The primary endpoint is the proportion (and percentage, %) of patients who claim preference of deferasirox FCT over deferasirox DT as measured by preference questionnaire at Week 48.

The analysis of primary variable will be based on the FAS.

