### **2.5.4 Supportive analyses**

Sensitivity analyses and supportive analyses will be conducted in order to provide evidence that the results seen from the primary analysis are robust.

In order to support the Mc Nemar's test for matched pair, the Odd's Ratio (OR) of patient preference (i.e.  $OR=p_{12}/p_{21}$ ), 95% CI and p-values will also be presented. Conditional logistic model for matched pair analyses may also be fitted if feasible.

The primary and above supportive analyses will also be performed for each subgroup of the baseline factor, i.e. on patients with TDT or NTDT and also on prior treatment status of iron chelation (naïve or pre-treated). Additionally, the primary analysis will be performed by age groups: 2-6 years (infant), 7-11 years (child), 12-17 years (adolescent), < 18 years (overall of infant, child and adolescent), and  $\geq 18$  years (adult). No p-values will be presented for subgroup analyses.

To identify the impact of preference on switching, the primary analyses will be performed separately for patients with or without switching before Week 48.

As a supportive analysis, the primary analysis will also be provided for PPS.

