| G01                 | Patients not completed the safety follow up evaluation  | INCLUDE IN EVERYTHING        | 0                    |
| G02a                | Patient did not complete the preference questionnaire in each period (W28 and W48)  | INCLUDE IN EVERYTHING        | 0                    |
| G02b                | Patient did not complete/partially complete the preference questionnaire at the required visits as per protocol (for W4, W24, W28 and W48)  | INCLUDE IN EVERYTHING        | 0                    |
| G02c                | Patient did not complete/partially complete the preference questionnaire at immediate next visit after unplanned treatment switch protocol. | INCLUDE IN EVERYTHING        | 0                    |
| G03                 | Do not have the pill counting information for deferasirox FCT   | INCLUDE IN EVERYTHING        | 0                    |
| G04                 | Do not have the pill counting information for deferasirox DT  | INCLUDE IN EVERYTHING        | 0                    |
| G05                 | Non-Compliance with safety/serious adverse event (SAE) reporting as per protocol.   | INCLUDE IN EVERYTHING        | 0                    |
| G06                 | Patient did not completed/partially completed the SICT, Palatability, GI symptoms questionnaire (for W1, W4, W24, W28 and W48)              | INCLUDE IN EVERYTHING        | 0                    |
| G07                 | Any protocol deviation identified non GCP compliant as per protocol.  | INCLUDE IN EVERYTHING        | 0                    |
| G08                 | Missing Lab Parameters for Lab Biochemistry at 2 consecutive Visits   | INCLUDE IN EVERYTHING        | 0                    |
| G09                 | Missing Lab Parameters for Lab Biochemistry at Visit 9 or Visit 15  | INCLUDE IN EVERYTHING        | 0                    |
| G10                 | Missing Lab Parameters for Lab Hematology at 2 consecutive Visits   | INCLUDE IN EVERYTHING        | 0                    |
| G11                 | Missing Lab Parameters for Lab Hematology at Visit 9 or Visit 15  | INCLUDE IN EVERYTHING        | 0                    |
| G12                 | Missing Lab Parameters for Lab Urinalysis at 2 consecutive Visits.  | INCLUDE IN EVERYTHING        | 0                    |
| G13                 | Missing Lab Parameters for Lab urinalysis at Visit 9 or Visit 15  | INCLUDE IN EVERYTHING        | 0                    |

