| G14                 | Serum pregnancy test not done at Visit 15 in females of child bearing potential   | INCLUDE IN EVERYTHING        | 0                    |
| G15                 | Urine pregnancy test not done at Visit 2 in females of child bearing potential  | INCLUDE IN EVERYTHING        | 0                    |
| G16                 | Full visit is missing.  | EXCLUDE FROM PPS             | 4                    |
| G17                 | The visit has been performed out of protocol window.  | INCLUDE IN EVERYTHING        | 0                    |

| Deviation ID | Description of Deviation   | Exclusion in Analyses | Severity code |
|---------------------|---|------------------------------|----------------------|
| G18                 | Patient did not complete/partially complete the preference questionnaire at the immediate next visit after treatment switch.  | INCLUDE IN EVERYTHING        | 0                    |
| G19                 | Hepatitis B or Hepatitis C tests were not performed at visit 15   | INCLUDE IN EVERYTHING        | 0                    |
| G20                 | Treatment start date is outside the window period without an official medical interruption.   | EXCLUDE FROM PPS             | 4                    |
| G21                 | Ocular Examination was not performed  | INCLUDE IN EVERYTHING        | 0                    |
| G22                 | Audiometric Examination was not performed   | INCLUDE IN EVERYTHING        | 0                    |
| I01a                | ICF is not obtained from Subject.   | EXCLUDE FROM FAS AND SAF     | 3                    |
| I01b                | ICF is not obtained from Parent(s) or Legal patient(s) representative.  | EXCLUDE FROM FAS AND SAF     | 3                    |
| I01c                | Missing informed consent date for Subject.  | INCLUDE IN EVERYTHING        | 0                    |
| I01d                | Missing informed consent date from parent(s) or legal patient's representative.   | INCLUDE IN EVERYTHING        | 0                    |
| I02                 | Subject is < 2 years or age missing   | EXCLUDE FROM PPS             | 4                    |
| I03a                | Subjects being treated with Deferasirox during the 6 months within study participation.   | EXCLUDE FROM PPS             | 4                    |

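### Deviation G16 has no phase limit, so a visit missed after Week 48 can remove a patient from the Per-Protocol repeat of the Week 48 preference analysis

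*SAP*

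**What the plan says.** In SAP Section 5.5, Table 1, row G16 reads in full "Full visit is missing". Its action is exclusion from the PPS, severity code 4, and Table 2 of that section confirms that code 4 removes a patient from the PPS. SAP Section 2.2 states the general rule, "Any major protocol deviation will lead to exclusion of patients from PPS", and refers to Section 5.5 for the list. It sets no date after which deviations stop counting.

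The PPS has a specific use. SAP Section 2.5.4 says "As a supportive analysis, the primary analysis will also be provided for PPS". Under Section 2.5.1 the endpoint is the proportion of patients "who claim preference of deferasirox FCT over deferasirox DT as measured by preference questionnaire at Week 48", which is Visit 15.

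The visit windows in SAP Section 2.1.1 run well past that point. For example, "Visit 26 Date of visit should be 644 days from Visit 2", and Visit 777 follows at 672 days. Protocol Section 4.1 makes the extension optional.

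There are two database locks. SAP Section 2.1 plans one once all patients have completed their Week 48 assessments, and then: "A final database lock will occur when all patients have completed the study". SAP Section 2.14 places the primary analysis at the first lock and limits the accompanying baseline, efficacy and safety analyses to the core phase.

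**The concern.** A per-protocol set for a Week 48 outcome should be defined by what happened up to Week 48. If missing Week 60 counts as a disqualifying deviation, the set is selected partly on behaviour that followed the outcome and cannot have affected it.

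The PPS is the only alternative analysis set on which the primary analysis is repeated. If its membership can shift with later attendance, agreement or disagreement with the Full Analysis Set (FAS) result becomes harder to interpret. The same Week 48 analysis could also give one PPS result at the first lock and another at the final lock, with no change in the endpoint data.

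**Working it through.** **1. Is a limit implied by the table?** Comparing G16 with other rows of Table 1:

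| Row | Limit stated | Action |
|---|---|---|
| G08, G10, G12 (missing laboratory data) | two consecutive visits | include |
| G09, G11, G13 (missing laboratory data) | Visit 9 or Visit 15 | include |
| G14, G19 (tests not done) | Visit 15 | include |
| S06 (wrong formulation by error) | period 2 or extension phase | exclude from FAS |
| G16 (missed visit) | none | exclude from PPS |

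The table states a count or a visit where one is meant, and S06 shows that it is not confined to the core phase. G16 therefore has no implied limit. One missed visit is enough, in either phase.

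**2. Does the Week 48 lock keep extension visits out?** Not by itself. The protocol's amendment rationale reports 92 patients enrolled by 22 October 2018. Adding 672 days (Week 96) gives 24 August 2020, or 21 September 2020 if a 28-day screening period is added. The SAP document history labels the version of 4 September 2020 as preceding the interim lock. Up to 92 patients could thus have most or all of their extension visits on record at that lock.

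**3. How many visits can trigger exclusion?** For a patient who has Week 48 data, Visit 15 was attended by definition.

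- Core visits after baseline and before the endpoint: Visits 3 to 14 = 12.
- Post-endpoint visits: Visits 16 to 26 (11) plus Visit 777 (1) = 12.
- Total as the row is written: 24, twice the core count.

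**4. Starting number.** The plan's figure of 130 patients at Week 48 (SAP Section 3) is used as the base. It reproduces with the unpooled-variance McNemar formula:

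N = (1.960 + 0.842)² × (0.70 − 0.20²) / 0.20² = 7.849 × 16.5 = 129.5, rounded up to 130.

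Allowing for 10% missing, 130 / 0.9 = 144.4, which rounds up to 145, as the plan states.

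**5. Size.** The documents give no missed-visit rate, so the per-visit probability m is an assumption. With independent misses, and every patient entering and completing the extension, the excluded fraction is 1 − (1 − m)^k.

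| m | k = 12 (Visits 3–14) | k = 24 (as written) | Left of 130, k = 12 | Left of 130, k = 24 |
|---|---|---|---|---|
| 0.5% | 5.8% | 11.3% | 122 | 115 |
| 1% | 11.4% | 21.4% | 115 | 102 |
| 2% | 21.5% | 38.4% | 102 | 80 |
| 5% | 46.0% | 70.8% | 70 | 38 |

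The part that belongs to this point is the step from k = 12 to k = 24: about 13 patients at 1% (115 − 102) and 22 at 2% (102 − 80).

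If only half the patients completed the extension and the rest had no extension visits due, the excluded fraction would be the midpoint of the two columns. That is (11.4 + 21.4) / 2 = 16.4% at 1%, and (21.5 + 38.4) / 2 = 30.0% at 2%.

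**The case against.** The strongest reply is that a core-only count was probably intended. The primary analysis belongs to the Week 48 lock, and SAP Section 2.14 confines the accompanying analyses to the core phase. Other visit-specific rows in the G series go no later than Visit 15, and S06 names the extension explicitly where G16 does not. No section says that the PPS analysis is repeated, or its membership re-derived, at the final lock. This has force, and it is why the point says the result *can* depend on later events. It does not settle the matter, because nothing in the SAP limits which deviations count. The dates above show only that extension data could exist at the interim lock, not that they would be used.

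Four stronger readings are tempting, and the documents do not support them.

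- **G16 drops patients who have the endpoint while G02a keeps those who do not.** Row G02a (preference questionnaire not completed) does include the patient everywhere. However, SAP Section 2.5.2 restricts the test to patients who answered question 2, so a patient without a Week 48 answer contributes nothing to it in either set.
- **Missed visits should count only at Visits 9, 10 and 15.** Patients return every four weeks for study medication and assessments (Protocol Section 4.1), so a wholly missed core visit can bear on exposure. Requiring all core visits is strict but defensible. A three-visit rule would keep a patient who missed every visit from 3 to 8.
- **The rule favours FCT.** All planned extension treatment is FCT, so attendance could be related to preference, but the documents establish no direction.
- **The primary result is at risk.** Code 4 does not touch the FAS, on which the primary analysis rests.

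**Conclusion.** The point holds as a defect in the wording of one exclusion rule. As written, G16 lets a visit missed after Week 48 remove a patient from a Week 48 supportive analysis, and PPS membership could differ between the two locks.

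The consequence is confined to the PPS. Its size cannot be derived from the documents. The 11% to 21% (at 1%) and 22% to 38% (at 2%) comparisons assume a per-visit rate, independence across visits and full extension participation. Incomplete participation would reduce the post-endpoint part, and clustering of misses within patients would lower the overall exclusion. The figures indicate scale and are not a forecast. The row should be corrected, but it does not undermine the trial's main conclusion.

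**What to change.** Reword G16 in SAP Section 5.5, Table 1, to *full visit missing on or before Visit 15 (Week 48)*, keeping code 4. Add one sentence to SAP Section 2.2 stating that PPS membership for the Week 48 preference analysis is fixed on deviations dated up to Visit 15 and is not re-derived at the final lock.

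The cost is one table row and one sentence. No data collection changes, and the rule stays as strict as it now is for core visits. If the sponsor does want extension attendance to define a per-protocol population for extension analyses, that can be a separate, labelled rule.
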